10.0 Efficacy Analyses

All efficacy analyses will be based on the mITT Population, unless otherwise specified. Note that the use of the phrase "AF" or "AF episode" in the section and subsections below implies an occurrence of either atrial fibrillation or atrial flutter. Other analyses will be conducted to assess only atrial fibrillation, only atrial flutter, only atrial tachycardia, and a combination of either atrial fibrillation, atrial flutter, or atrial tachycardia.

Each participant will be continuously monitored for the first 30 days post-surgery, and during the first 7 days following Day 60, Day 90, Day 180, Day 270, and Day 360 visits, for all occurrences of AF episodes as well as the length of time spent in each of the corresponding AF episodes using ECG patches (ePatch) placed on the participant's chest.

Even though each participant is expected to wear the epatch for the first 30 days post-surgery, and during the first 7 days following Day 60, Day 90, Day 180, Day 270 and Day 360 visits, all analyzable data (interpretable) collected from the epatch will be included in the analysis regardless of any deviations from these timeframes.

The ECG measurements collected for AF episodes post-surgery will be used to provide 10 different definitions for POAF for use in statistical analyses, namely:

- 1. at least 1 continuous AF episode \geq 30 seconds
- 2. at least 1 continuous AF episode \geq 2 minutes

- 3. at least 1 continuous AF episode \geq 5 minutes
- 4. at least 1 continuous AF episode ≥ 6 minutes
- 5. at least 1 continuous AF episode \geq 30 minutes
- 6. at least 1 continuous AF episode \geq 1 hour
- 7. at least 1 continuous AF episode \geq 4 hours
- 8. at least 1 continuous AF episode ≥ 6 hours
- 9. at least 1 continuous AF episode \geq 12 hours
- 10. at least 1 continuous AF episode \geq 24 hours

Based on information collected from continuous monitoring for all occurrences of AF during the first 30 days post-surgery, the percent of time spent in AF (hereinafter referred to as AF Burden) during the first 30 days post-surgery will be calculated as (the total time spent in AF during the first 30 days post-surgery divided by the total time of analyzable data obtained from the ECG patch during the first 30 days post- surgery) multiplied by 100.

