The following five binary (yes/no) variables will be used to analyze the need for pharmacologic and/or procedural intervention due to AF during the first 30 days post-surgery:

- 1. at least one pharmacologic intervention (i.e., anticoagulation or antiarrhythmic drugs)?
- 2. at least one anticoagulation pharmacologic intervention?
- 3. at least one antiarrhythmic pharmacologic intervention?
- 4. at least one procedural intervention (see list in Section 8.0)?
- 5. at least one pharmacologic or procedural intervention?

In addition, time to event variables will also be created for each of the corresponding 5 variables above. The time to the first event will be used for analysis. All these variables will be analyzed using the same methods for similar variables in Sections 10.1 and 10.2.

The need for pharmacologic and/or procedural intervention due to AF from Day 31 to Day 360 post-surgery will be analyzed in a similar fashion. Participants with no events who exit the study prior to Day 360 will be censored at their respective study exit day minus 30 days, while participants with no events who exit the study on or beyond day 360 will be censored at day 330 (360 - 30 = 330). Pharmacologic and/or procedural interventions due to AF with onset dates prior to day 31 that are ongoing at day 31 will count as events for these endpoints, with a time-to-event equal to zero.

Descriptive statistics will be presented by treatment group for each of the following:

- time to POAF resolution from first dose of prescription of pharmacologic intervention
- time to POAF resolution from first procedural intervention
- types of pharmacologic interventions used due to POAF

- will be further categorized by "medication of interest" (antiarrhythmics versus anticoagulants) as defined in Section 8.0 above.
- yes/no: Beta blocking agent (ATC code: C07A) withdrawn within 3 days post-surgery and no replacement (no new beta blocker prescription) within 7 days post-surgery

Other Efficacy Variables

- Percentage of participants with clinically important tachycardia in AF (defined as heart rate ≥ 100 bpm for at least 2 minutes) within 30 days post-surgery
- Percentage of participants with any occurrence of AF as defined in the primary and secondary endpoints during the first 7 days following Day 60, Day 90, Day 180, Day 270, and Day 360 visits

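### The Day 31 to Day 360 intervention endpoints have no at-risk set: event-free exits before Day 30 get negative censoring times, and the binary version leaves early leavers unclassified

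*SAP*

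**What the plan says.** SAP 10.3 (Need for Medical or Procedural Intervention Due to AF) defines five yes/no variables for the first 30 days and a matching time-to-event variable for each. On method it says: "All these variables will be analyzed using the same methods for similar variables in Sections 10.1 and 10.2". That means the stratified CMH test for the binary variables, and Kaplan-Meier, log-rank and Cox for the times. It then extends the set to the late period: need "due to AF from Day 31 to Day 360 post-surgery will be analyzed in a similar fashion".

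Three timing rules follow for the late period:

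- Exit before Day 360 without an event: "Participants with no events who exit the study prior to Day 360 will be censored at their respective study exit day minus 30 days".
- Exit on or after Day 360 without an event: these participants "will be censored at day 330 (360 - 30 = 330").
- Interventions begun before Day 31 "that are ongoing at day 31 will count as events for these endpoints, with a time-to-event equal to zero".

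No separate analysis set is named, so SAP 10.0 governs: "All efficacy analyses will be based on the mITT Population, unless otherwise specified". Under SAP 6.1, a treated, randomised participant enters the mITT with a single patch ECG after dosing, up to Day 30. Remaining in the study to Day 31 is not required. The no-imputation statement in SAP 10.0 concerns patch data only. The SAP has no missing-data rule for the intervention yes/no variables.

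**The concern.** There are two separate gaps, and neither causes the other.

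First, subtracting 30 moves the time origin to Day 30, but the rule applies to everyone who exits before Day 360, including those who leave before that origin. Their time is negative, which is not a valid follow-up time. The SAP does not tell the programmer whether to leave it, drop it or recode it.

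Second, a late-period percentage on the full mITT keeps people in the denominator who were never observed in the window. If they are recorded as having had no intervention, early death or withdrawal counts as not needing late AF treatment.

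The carry-over rule adds an ambiguity. For someone who exits on Day 12, the SAP does not say whether an AF drug record with no stop date is ongoing at Day 31, and so an event at time zero. The same exit without such a record gives a negative time. Neither participant was observed in the window.

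The paragraph governs five binary and five time-to-event variables, each compared with placebo for two doses: (5 + 5) x 2 = 20 comparisons.

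**Working it through.** **Inputs from the documents.** The three timing rules are from SAP 10.3. The randomised total of about 330 in a 1:1:1 ratio gives 330 / 3 = 110 per arm. SAP 13.0 assumes about 10% early dropout in each arm, in relation to completing assessments to Day 60: 0.10 x 110 = 11. The documents do not give the share leaving before Day 31 or the rate of late intervention. Both are assumptions below.

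**Step 1. The plan's own figure.** Maximum time = 360 - 30 = 330, which reproduces.

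**Step 2. The same rule at earlier exits.** Time = exit day - 30.

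| Exit day | 1 | 12 | 15 | 29 | 30 | 31 | 359 | 360 or later |
|---|---|---|---|---|---|---|---|---|
| Time | -29 | -18 | -15 | -1 | 0 | 1 | 329 | 330 |

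Every event-free exit on Days 1 to 29 is negative. Such exits are foreseeable: SAP 9.0 tabulates study duration from 6 and 14 days upward.

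**Step 3. Effect on the time-to-event analyses.** All events in this window have time 0 or later. A participant censored below 0 is in no risk set at any event time, so contributes nothing to the Kaplan-Meier steps, the log-rank sums or the Cox partial likelihood. The argument also holds within strata. One simulated data set illustrates it, using an unstratified log-rank test with 110 per arm and 8 and 4 early leavers. The assumed time-zero event probabilities were 12% and 20%, with daily hazards of 0.0003 and 0.0004 afterwards.

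| Handling of negative times | N | Kaplan-Meier event percentage at 330, by arm | Log-rank chi-square |
|---|---|---|---|
| Left negative | 220 | 13.73, 38.68 | 16.57 |
| Excluded | 208 | 13.73, 38.68 | 16.57 |
| Set to 0 | 220 | 13.26, 37.95 | 17.21 |

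Leaving the times negative and excluding the participants agree in everything but N. Setting them to 0 differs because those people join the risk set for the carry-over events at time zero.

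**Step 4. Effect on the binary analysis if early leavers are coded No.** Let p be the late need among those at risk and e the early leavers of 110. The reported rate is p x (110 - e) / 110, so the understatement is p x e / 110.

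- Low end: p = 10%, e = 2: 0.10 x 2 / 110 = 0.18 points.
- Middle: p = 20%, e = 6: 0.20 x 6 / 110 = 1.09 points.
- High end: p = 30%, e = 11 (the whole 10% dropout falling before Day 31): 0.30 x 11 / 110 = 3.0 points.

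**Step 5. Between-arm effect.** With p equal in both arms, the spurious difference is p x (difference in e) / 110. It is zero when e is equal. For 2 against 8 early leavers it is 0.20 x 6 / 110 = 1.09 points at 20% need and 0.30 x 6 / 110 = 1.64 points at 30%. The standard error of a difference at 30% with 110 per arm is sqrt(2 x 0.30 x 0.70 / 110) = 6.2 points, so 1.64 points is about 0.3 standard errors.

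**The case against.** The strongest reply is that the practical harm is small. Step 3 shows that for Kaplan-Meier, log-rank and Cox, the rule taken literally gives the same answer as the restricted set proposed here. Nothing in the SAP tells anyone to set negative times to 0. This stands: for those analyses the defect is an invalid rule and an unclear N, with a changed result only under one kind of repair.

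A reader might also infer that the SAP counts early leavers as not needing treatment, or that the minus-30 rule brings this about. The documents support neither. No section classifies these participants as No, missing or excluded. Any coding would follow from the full mITT denominator, and correcting the censoring rule would leave that question open.

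Nor do the documents support a definite between-arm bias. SAP 13.0 assumes the same dropout in each arm, and an imbalance such as 2 against 8 has no source in them.

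Two further points narrow the issue. SAP 15.6.2 completes a partly missing stop date, and when its month and year match the study exit it assigns the exit day. That closes some AF drug records before Day 31, but not a record with no stop date at all. SAP 7.0 and 9.0 already tabulate discontinuation reasons and study duration of at least 30 days by arm. An imbalance in early exit would therefore be visible, though reasons are not split at Day 30.

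None of this supplies the missing at-risk condition or the missing binary classification.

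**Conclusion.** The concern holds in limited form. The negative times follow directly from the stated rule and the mITT definition, and no other section prevents them. The binary gap is real as an omission. Its effect depends on a coding choice that the SAP does not state.

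If early leavers are coded No, each arm's late-period percentage is understated by about 0.2 to 3.0 points. This rests on assumed late need of 10% to 30% and on 2 to 11 of 110 leaving before Day 31. The mITT may be somewhat smaller than 110 per arm. A between-arm distortion needs unequal early exit as well, and in the example above it is small against sampling error.

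These are additional efficacy variables, for which SAP 10.0 makes no multiplicity adjustment. The primary and secondary results are untouched. The change is still worth making, because a written rule should not produce impossible times or leave open who is in the denominator.

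**What to change.** In SAP 10.3, for both the binary and the time-to-event versions of the Day 31 to Day 360 intervention variables:

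1. Define the analysis set as mITT participants still in the study on Day 31. This removes the negative times and the zero time for a Day 30 exit.
2. Apply the carry-over rule for interventions ongoing at Day 31 only to that set.
3. Beside the table, give by arm the number who exited on or before Day 30, with reasons.
4. Keep the percentage of participants defined in Protocol 9.4.1.4 as the reported measure. A Kaplan-Meier estimate at time 330 may be added as supplementary, since it also deals with exits between Day 31 and Day 360. State how deaths are handled, because treating them as ordinary censoring assumes that they are non-informative.

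The cost is two or three sentences and one analysis flag. The downside is that the late comparison becomes conditional on being in the study at Day 31, a post-randomisation condition that the table should state.

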#### AGN-151607

E

4.	Contraceptives		
4.01	Male participants willing to minimize the risk of inducing pregnancy up to Day 60.		
	A male participant must agree to use contraception as detailed in Appendix 7, Section 10.7 of this protocol until Day 60 and refrain from donating sperm during this period.		
4.02	Female participants willing to minimize the risk of inducing pregnancy up to Day 60.		
	A female participant is eligible to participate if she is not pregnant (has a negative urine pregnancy result prior to randomization) not breastfeeding, and at least 1 of the following conditions applies:		
	a. Not a woman of childbearing potential (WOCBP) as defined in Appendix 7, Section 10.7		
	OR		
	b. A WOCBP who agrees to follow the contraceptive guidance in Appendix 7, Section 10.7 of this protocol until after Day 60.		
5.	Informed Consent		
5.01	Capable of giving signed informed consent as described in Appendix 1, Section 10.1, which includes compliance with the requirements and restrictions listed in the informed consent form (ICF) and in this protocol.		
5.02	Written informed consent from the participant has been obtained prior to any study-related procedures.		
5.03	Written documentation has been obtained in accordance with the relevant country and local privacy requirements, where applicable (eg, Written Authorization for Use and Release of Health and Research Study Information [US sites] and written Data Protection consent (European Union [EU] sites).		
6.	Other		
6.01	In sinus rhythm for the last 48 hours prior to randomization based on standard-of- care assessments and study ECGs (note: continuous ECG monitoring for 48 hours is not required; prior history of paroxysmal AF is acceptable).		
6.02	Willing to wear an ECG patch for a full 30 days post-surgery and for 7 days after each study visit		
6.03	Able, as assessed by the investigator, and willing to follow study instructions and likely to complete required study visit.		

AGN-151607

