### 6.5.1. Prohibited Interventions and Washout Before the Study

Participants must discontinue any of the medications listed in Table 6-2 for the specified period prior to surgery. Other medications being used at screening may be continued.

Drug Class/Treatment	Washout Required Prior to Surgery	
Class I or Class III antiarrhythmic drugs (eg, amiodarone)	At least 5 half-lives or 5 days, whichever is the longest. In the case of amiodarone, 90 days washout is required.	
All types of botulinum toxins	At least 6 months since last treatment with any botulinum toxin	

Table 6-2Prohibited Medications with Required Washout Period

AGN-151607

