#### Table 8-4 Assessment of Pharmacologic Therapies and/or Medical Procedures

Assessment	Timing	Measurement
Pharmacologic intervention (ie, anticoagulation, antiarrhythmic drugs)	Through Day 367	
 
Timing of prescription and whether it was prescribed due to occurrence of POAF
 
Length of prescription
 
Timing of AF resolution, if available
 

Procedural intervention (ie, cardioversion, pacemaker implantation, ablation, additional cardiac surgery)	Through Day 367	
 
Timing of procedure and whether it was assigned due to the occurrence of POAF
 
Timing of AF resolution, if available
 

AF = atrial fibrillation; POAF = post-operative atrial fibrillation

A composite endpoint composed of pharmacologic and procedural interventions will also be analyzed.

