# 9.4.1.4. Additional Efficacy Variables

The additional efficacy variables are:

- Percentage of participants with clinically important tachycardia in AF (defined as heart rate ≥ 100 bpm for at least 2 minutes
- Percentage of participants needing pharmacologic intervention (ie, anticoagulation, antiarrhythmic drugs) during the first 30 days post-surgery due to AF
- Percentage of participants needing pharmacologic intervention (ie, anticoagulation, antiarrhythmic drugs) from Day 31 to Day 360 post-surgery due to AF
- Percentage of participants needing procedural intervention (ie, cardioversion, ablation, additional surgery) during the first 30 days post-surgery due to AF
- Percentage of participants needing procedural intervention (ie, cardioversion, ablation, additional surgery) from Day 31 to Day 360 post-surgery due to AF
- Time to first prescription of pharmacologic intervention due to POAF during the first 30 days post-surgery and length of time that prescription is taken.
- Time of POAF resolution from first dose of prescription of pharmacologic intervention
- Time to first procedural intervention due to POAF during the first-30 days post-surgery.
- Time of POAF resolution from first procedural intervention due to AF
- Length of stay in ICU and reason
- Length of stay in hospital and reason
- Number of all-cause re-hospitalizations within 30 days post-discharge
- Number of non-arrhythmia cardiovascular re-hospitalizations within 30 days post-discharge
- Number of arrhythmia re-hospitalizations within 30 days post-discharge
- Binary measure (Y/N) of all-cause hospitalizations within 30 days post-discharge

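### SAP 10.3 counts AF treatment still ongoing at Day 31 as a Day 31-360 event, so the late variable mixes carried-over treatment with new late need and does not clearly exclude pre-surgery therapy

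*SAP*

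**What the plan says.** Protocol 9.4.1.4 lists need for drug and for procedural intervention twice, once for the first 30 days and once for Day 31 to Day 360. The late drug variable is: "Percentage of participants needing pharmacologic intervention (ie, anticoagulation, antiarrhythmic drugs) from Day 31 to Day 360 post-surgery due to AF".

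SAP 10.3 (Need for Medical or Procedural Intervention Due to AF) defines five yes/no variables for the first 30 days, one of them for anticoagulation alone, with matching time-to-first-event variables. It analyses the late window the same way and adds that "Pharmacologic and/or procedural interventions due to AF with onset dates prior to day 31 that are ongoing at day 31 will count as events", "with a time-to-event equal to zero". Participants without an event are censored at exit day minus 30, or at 330 if they reach Day 360. No analysis limited to treatment newly started after Day 30 is specified.

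On treatment before surgery, Protocol 5.1 (criterion 6.01) says that "prior history of paroxysmal AF is acceptable". Table 6-2 requires washout only for Class I/III antiarrhythmics and botulinum toxins, and Section 6.5.1 adds: "Other medications being used at screening may be continued".

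On attribution, Protocol 8.1.4.1 describes these interventions as responses to POAF, and Table 8-4 collects "Timing of prescription and whether it was prescribed due to occurrence of POAF". SAP 10.3 refers to AF in the carry-over rule, in actionable AF and in win-ratio component 4, but to POAF in its descriptive list of drug types. It does not say which attribution governs.

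**The concern.** Protocol 4.1 estimates the toxin's effect at 3 to 6 months and follows participants for 12 months. A reader will look to the late variable for evidence that benefit extends past Day 30. Under the carry-over rule, a difference can appear there because fewer treated participants had POAF in the first month, even if nothing differs afterwards. The Kaplan-Meier and Cox analyses then begin with a block of time-zero events fixed before the window opens.

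The missing lower limit on onset date works in the opposite direction. Treatment dating from before surgery should be balanced by randomization. If it counts, it adds events to every arm and pulls the comparison towards no difference.

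**Working it through.** **The plan's own figure.** The only number given for this variable is the censoring day, 360 - 30 = 330, which is correct. The documents state no event rate, carry-over rate or power for it, so every size below rests on assumed rates.

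**How the rule classifies participants**

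| Participant | First 30 days | Day 31-360 |
|---|---|---|
| Drug for POAF from Day 3, stopped Day 20 | event | no event |
| Drug for POAF from Day 3, still taken at Day 31, AF never returns | event | event at time 0 |
| First drug started Day 100 | no event | event at 100 - 30 = 70 (scale used for censoring) |
| Anticoagulant for paroxysmal AF since before surgery, continued | SAP silent | event at time 0 if AF is read literally; no event if the Table 8-4 POAF attribution applies |

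Row 2 is certain from the text. Row 4 depends on which attribution is used.

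**Early effect carried forward.** Let e be the share starting treatment by Day 30, o the share of those still on it at Day 31, and q the new-start rate among everyone else. Carry-over is c = e x o, and the late event rate is c + (1 - c) x q. Assumed: e = 30% placebo and 18% active; q = 5% in both arms.

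| o | Placebo | Active | Difference | Placebo events at time 0 |
|---|---|---|---|---|
| 25% | 7.5% + 92.5% x 5% = 12.125% | 4.5% + 95.5% x 5% = 9.275% | 2.85 points | 7.5/12.125 = 62% |
| 50% | 15% + 85% x 5% = 19.25% | 9% + 91% x 5% = 13.55% | 5.70 points | 15/19.25 = 78% |
| 75% | 22.5% + 77.5% x 5% = 26.375% | 13.5% + 86.5% x 5% = 17.825% | 8.55 points | 22.5/26.375 = 85% |

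The new-start rate is identical in both arms throughout.

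A second set of assumptions takes carry-over as 10% to 100% of the POAF rates in SAP 13.0 (47.8% and 27.8%), with q = 10% in both arms:
- At 10%: 4.78% + 95.22% x 10% = 14.3% versus 2.78% + 97.22% x 10% = 12.5%, relative risk 0.87.
- At 100%: 47.8% + 52.2% x 10% = 53.0% versus 27.8% + 72.2% x 10% = 35.0%, relative risk 0.66.
- Between these limits, 33% to 90% of placebo events fall at time zero.

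**Dilution by treatment common to all arms.** Assume a real late effect, q = 20% versus 10%, and an equal share g carried over in each arm. The rate is g + (1 - g) x q. Power is the two-sided 0.05 normal approximation at 100 per arm.

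| g | Placebo | Active | Relative risk | Power |
|---|---|---|---|---|
| 0% | 20.0% | 10.0% | 0.50 | 51% |
| 5% | 24.0% | 14.5% | 0.60 | 40% |
| 10% | 28.0% | 19.0% | 0.68 | 32% |
| 20% | 36.0% | 28.0% | 0.78 | 23% |
| 30% | 44.0% | 37.0% | 0.84 | 17% |

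The effect is diluted but still present.

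**Missing stop dates.** Under SAP 15.6.2, a stop date lacking month and day in the year of study exit is set to the exit date. This can turn a short course into one that is ongoing at Day 31.

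**The case against.** The strongest reply is that the protocol endpoint concerns participants *needing* intervention in the late window, not those newly starting it. Someone still on treatment at Day 31 fits that wording. In the middle row above, 15% versus 9% on treatment at Day 31 is a genuine randomized difference in treatment burden. This stands, and it is why the percentage should be kept and split rather than redefined.

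Second, Protocol 8.1.4.1 and Table 8-4 point to POAF, and both documents use AF and POAF side by side for these variables. Counting pre-surgery therapy is thus a gap in the SAP wording, not a declared intention. Washout of Class I/III antiarrhythmics and exclusion of permanent or persistent AF narrow the gap mainly to anticoagulants. This also stands, but the SAP sentence itself does not close the gap.

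Third, late AF is assessed elsewhere: by patch after the Day 60 to Day 360 visits, and as freedom from AF through 12 months off antiarrhythmics or off anticoagulants. That limits the consequence without making this variable interpretable.

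Three stronger readings are tempting and not supported:
- A reader might infer that any AF treatment begun before Day 31 counts. It must be ongoing at Day 31.
- A reader might infer that the variable cannot show a late benefit. New starts still count, and stopping before Day 31 lowers the count.
- A reader might infer a matching loss of power in the 30-day variables. The carry-over rule applies only to Day 31-360, and no SAP text says that a resumed pre-surgery drug counts in the first 30 days.

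**Conclusion.** The concern holds in a limited form. It is certain from SAP 10.3 that treatment begun for POAF in the first 30 days and ongoing at Day 31 is an event in both windows, at time zero in the later one, and that nothing planned isolates new late need. It is a matter of wording, to be settled before analysis, whether anticoagulation dating from before surgery also counts.

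Under the assumed rates, early treatment alone produces a late difference of 2.85 to 8.55 points (19.25% versus 13.55% in the middle case). Equal carry-over of 5% to 30% moves a true relative risk of 0.50 to between 0.60 and 0.84. These are illustrations, since the documents supply none of the rates.

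The primary and secondary variables are untouched. The affected variables are additional ones without multiplicity adjustment. The procedural variable is hardly affected, because the procedures listed in SAP 8.0 are discrete events.

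**What to change.** 1. In SAP 10.3, count an intervention only if it started after the study injection, or was restarted because of POAF, using the Table 8-4 POAF attribution. Uninterrupted or routine continuation of a pre-surgery AF drug is not an event. Use the same definition for actionable AF and win-ratio component 4.
2. Keep the Day 31-360 percentage but report it on two lines with the mITT denominator: carried over from Days 1-30, and newly started on or after Day 31. In the middle example these lines would read 15% versus 9%, and 85% x 5% = 4.25% versus 91% x 5% = 4.55%, which shows where the difference arises. Being untreated at Day 31 is a post-randomization state, so the second line should be read beside the first and not as a stand-alone comparison.
3. Add, as a supplement and not a replacement, time to first intervention from surgery to Day 360 in the full mITT set. This also avoids the negative censoring times that exit day minus 30 gives to anyone leaving before Day 30 (for example, 20 - 30 = -10).

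Start dates and POAF attribution are already collected. The cost is SAP wording, a little more programming, and fewer events in the late variable.

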# 9.4.1.5. Secondary and Additional Efficacy Analyses

For each efficacy variable with binary categorical response outcome, the response proportions will be analyzed using the same methods used to analyze the primary efficacy variable.

Kaplan-Meier curves for time to event data will be produced by treatment group and compared using the log-rank test. Time to event data will also be compared between treatment groups using Cox proportional hazards models.

ICU and hospital length of stay will be compared between groups using t-tests as well as linear regression models with adjustment for POAF baseline risk factors. The data in both groups will first be examined for normality. Should the data have a normal distribution, it will be analyzed using an unadjusted t-test. In the event of significant skewedness, the Wilcoxon rank-sum test will be used.

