In addition, similar definitions of POAF as well as the derivation of the AF Burden will be obtained based on continuous monitoring of all occurrences of AF during the first 7 days following Day 60, Day 90, Day 180, Day 270, and Day 360 visits.

All analyses using ECG patch data will be based on observed data; no imputation will be performed on missing data from the ECG patch device. Descriptive statistics of the total time of analyzable data obtained from the ECG patch during the first 30 days post- surgery will be presented by treatment group. Similar statistics will be presented for each of the first 7 days following Day 60, Day 90, Day 180, Day 270, and Day 360 visits.

Unless otherwise stated, the ICU admission date for the index surgery (initial care of indication under study) will be used as reference timepoint to establish if an event occurred within a specified timeframe "post-surgery". For example, the occurrence of AF during the first 30 days post-surgery will imply the occurrence of AF during the first 30 days following the initial ICU admission date.

In general, continuous and ordinal variables will be summarized by descriptive statistics and will include sample size, mean, standard deviation, median, minimum, and maximum. Nominal variables will be summarized by frequency and percentage.

Inferential analyses will include 3 treatment groups: Placebo, 125 U, and 250 U of AGN-151607. Each dose level of AGN-151607 (125 U and 250 U) will be separately compared to placebo. All treatment comparisons will be made at the $\alpha = 0.05$ level (2-sided). To control for multiplicity in comparing 2 doses of AGN-151607 with placebo, the primary efficacy variable will be tested sequentially by first comparing the high dose to placebo. The low dose will be compared to

placebo only if the comparison to the high dose is found to be statistically significant. There will be no adjustment for multiple comparisons for all other efficacy variables.

Mis-stratified participants, if any, will be analyzed based on the correct stratification group [type of surgery (presence or absence of valve surgery) and age group (< 65 or ≥ 65 years)], not the stratification group to which the participants were assigned at the time of randomization.

Unless otherwise stated, the use of the phrase "percentage of participants" for any efficacy variable in the sections below assumes the variable is a binary categorical response outcome.

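### Time to POAF resolution after intervention gets only descriptive statistics in the SAP, with no definition of resolution, denominator or censoring rule, and the drug clock can start at an anticoagulant

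*SAP*

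**What the plan says.** Protocol Section 9.4.1.4 lists two resolution times as additional efficacy variables: one from the first dose of a drug intervention, and "Time of POAF resolution from first procedural intervention due to AF". Section 9.4.1.5, which covers secondary and additional analyses, states: "Kaplan-Meier curves for time to event data will be produced by treatment group and compared using the log-rank test". It adds Cox models. Table 8-4 sets out what is collected, including "Timing of AF resolution, if available".

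SAP Section 10.3 carries both variables forward, the first as "time to POAF resolution from first dose of prescription of pharmacologic intervention". The sentence that governs them is "Descriptive statistics will be presented by treatment group for each of the following". SAP Section 10.0 says what that means for a continuous variable: "continuous and ordinal variables will be summarized by descriptive statistics and will include sample size, mean, standard deviation, median, minimum, and maximum". It also says of patch data that "no imputation will be performed on missing data from the ECG patch device".

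In the same part of Section 10.3, the first of the five need-for-intervention variables is "at least one pharmacologic intervention (i.e., anticoagulation or antiarrhythmic drugs"), so a drug intervention may be of either kind. The split into antiarrhythmics and anticoagulants is attached to the tabulation of intervention types, not to the resolution time.

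**The concern.** A resolution time is missing for exactly those participants whose AF was not seen to end: those who died, left the study or were still in AF when monitoring stopped. A mean or median needs a value for each person. Without a censoring rule the summary falls back on those who have one, and long durations are under-represented. If the share of unresolved AF differs between arms, part or all of that difference disappears from the table.

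The start of the drug clock adds a second problem. The protocol heads its anticoagulation section (6.5.5) with stroke prevention, so a time counted from an anticoagulant dose and a time counted from an antiarrhythmic dose have different meanings. Nothing requires AF to be ongoing at that dose, so a negative or undefined time is possible.

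At stake is how the trial describes the duration of treated POAF, which is part of the burden these endpoints are meant to capture.

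**Working it through.** The plan states no figure for these variables, so there is none to reproduce. The check has two parts.

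**1. Does the text keep unresolved cases in?**

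- Five need-for-intervention variables, SAP Section 10.3: time-to-event versions are analysed by the Section 10.1 and 10.2 methods, with explicit censoring for Day 31 to Day 360.
- Time to rehospitalization, SAP Section 10.3: Kaplan-Meier, with censoring at study exit.
- The two resolution times, same section: outside both of those provisions, with descriptive statistics only.
- Monitoring: the patch is worn for 30 days after surgery and then for 7 days after each of the Day 60, 90, 180, 270 and 360 visits. AF still running when the first period stops has no patch-observed end.
- SAP Section 16.0: lists dropping the logistic regression, replacing t-tests by ANOVA for length of stay, and adding the 6-minute definition. It does not mention resolution time.

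The contrast with the neighbouring variables makes it unlikely that descriptive statistics is shorthand for Kaplan-Meier. No rule keeps an unresolved participant in the summary.

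**2. How large could the effect be?**

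The share u with no observed resolution is not in the documents. It is assumed here to be 5% to 40%.

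*Model A: exponential resolution, common observation window T.* The rate is λ = −ln(u)/T.

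- Censored (Kaplan-Meier) median = ln 2 / λ
- Median among resolved cases = −ln((1+u)/2) / λ
- Ratio = −ln((1+u)/2) / ln 2, which does not depend on T

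| u | ratio | resolved-only median too short by |
|---|---|---|
| 5% | 0.93 | 7% |
| 10% | 0.86 | 14% |
| 20% | 0.74 | 26% |
| 30% | 0.62 | 38% |
| 40% | 0.51 | 49% |

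With u = 30% and T = 28 days, λ = 1.204/28 = 0.0430 per day. The censored median is 0.693/0.0430 = 16.1 days and the resolved-only median is 0.431/0.0430 = 10.0 days.

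For two arms with 30% and 10% unresolved, the censored medians are 0.58T and 0.30T (ratio 1.91). The resolved-only medians are 0.36T and 0.26T (ratio 1.38). The contrast shrinks but keeps its direction.

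*Model B: a share u never resolves; the rest are exponential with median 1.00 day.* The all-treated median is −ln((0.5−u)/(1−u)) / ln 2.

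| u | resolved-only median (days) | all-treated median (days) |
|---|---|---|
| 10% | 1.00 | 1.17 |
| 20% | 1.00 | 1.42 |
| 30% | 1.00 | 1.81 |
| 40% | 1.00 | 2.58 |

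Here two arms with different unresolved shares give the same resolved-only median, so the contrast is hidden. This follows from giving resolvers in both arms the same time distribution.

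**Who contributes.** At the planning rates of 47.8% and 27.8% (SAP Section 13.0), at most about 48 placebo and 28 active participants per 100 would have POAF, and only those who are treated for it enter the summary.

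**The case against.** The strongest reply is that this is a drafting gap in minor descriptive variables. Several parts of it stand.

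- A reader might infer that the SAP restricts the summary to participants whose AF resolved. No sentence says so. The words in Table 8-4 describe data collection and are not an exclusion rule. Restriction is the natural consequence of summarising observed values, but it remains an inference.
- A reader might say that refractory AF simply vanishes. That depends on the undefined term. If the end of an episode counts as resolution, AF that stops and returns stays in. The sample size is also reported, and the same section counts participants needing intervention. Comparing the two counts would show a shortfall, but not whether it is unresolved AF or missing data.
- A reader might fault the variable for not measuring response to rescue treatment. Protocol Section 8.1.4.1 gives the purpose as assessing the burden of POAF, so the plan makes no such claim. A duration biased short would still understate burden.
- The anticoagulant point concerns only the drug variable, and its broad start point is already in the protocol. It is not an SAP departure.
- Kaplan-Meier would not make the comparison randomised. Treatment is at investigator discretion in participants who have already developed POAF.

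It can also be said that Section 9.4.1.5 of the protocol does not name these variables. Its heading covers the additional variables, however, and a time whose end may go unobserved is time-to-event data in the ordinary sense.

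**Conclusion.** The point holds as a minor one. Followed as written, the SAP gives no value to AF with no observed end, and the method differs from the protocol without being listed as a change. The 7% to 49% shortening rests on an exponential model and an assumed unresolved share, so it illustrates the size and does not predict it. Whether a difference between arms is attenuated (Model A) or hidden (Model B) also depends on the model. The documents do not support a claim that it would always be erased or reversed.

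The drug clock's start point is a separate ambiguity in that one variable. Both variables are additional endpoints with no test planned in the SAP and no decision attached to them.

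**What to change.** In SAP Section 10.3:

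- Define resolution as the end of the AF episode that was ongoing at the intervention.
- Report by arm the numbers treated, resolved, unresolved, and with an episode that had ended before the intervention.
- Present Kaplan-Meier curves, or cumulative incidence with death as a competing event. Censor unresolved participants at the last analyzable patch time or at exit.
- For the drug variable, present antiarrhythmic starts separately from anticoagulant-only starts.
- Label the comparison between arms as descriptive, because it covers a post-randomisation subset.
- List in Section 16.0 any remaining departure from protocol Section 9.4.1.5, or from the start point in Section 9.4.1.4.

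The inputs are already planned: medication dates and times (protocol Section 6.5.3), procedure timing (Table 8-4) and AF episode lengths from the patch (SAP Section 10.0). The cost is SAP wording, extra programming and fewer participants in the antiarrhythmic analysis.
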